11.3	SUBJECT STIPENDS OR PAYMENTS	1748
13	PUBLICATION PLAN.....	1748
14	REFERENCES.....	1849

List of Abbreviations

AE	Adverse Event
ALK Phos	Alkaline Phosphatase
ALT	Alanine Aminotrasferase
AST	Aspartate Transaminase
AUROC	Area Under Receiver Operating Characteristic (Curve)
CBC	Complete Blood Count
CKD	Chronic Kidney Disease
CMP	Comprehensive Metabolic Panel
CNI	Calcineurin Inhibitor
CRF	Case Report Form
Cr	Creatinine
CTC	Comprehensive Transplant Center
eCRF	Electronic Case Report Form
eGFR	Estimated Glomerular Filtration Rate
FDA	Food and Drug Administration
GCP	Good Clinical Practice
GFR	Glomerular Filtration Rate
GGT	Gamma-Glutamyl Transpeptidase
HBV	Hepatitis B Virus
HCV	Hepatitis C Virus
HbA1C	Hemoglobin
HIPAA	Health Insurance Portability and Accountability Act of 1996
HIV	Human Immune Deficiency Virus

I/E	Inclusion/Exclusion
ICH	International Conference on Harmonization
IHC	Immunohistochemical
IL-2	Interleukin 2
IM	Immune Monitoring
IRB	Institutional Review Board
IS	Immunosuppression
ITN	Immune Tolerance Network
LFT	Liver Function Tests
LT	Liver Transplant
MDRD-4	Modification of Diet in Renal Disease-4 (version four)
MLR	Mixed Lymphocyte Reaction
NIAID	National Institute of Allergy and Infectious Disease
NIH	National Institutes of Health
NUIRB	Northwestern University Institutional Review Board
OLT	Orthotopic Liver Transplant
PBMC	Peripheral Blood Mononuclear Cell
PI	Principal Investigator
pLTQ	Post Liver Transplantation Quality of Life Instrument
PTLD	Post Transplant Lymphoproliferative Disorder
QOL	Quality of Life
RM-ANOVA	Repeated Measures o fAnalysis of Variance
SAE	Serious Adverse Event
SRL	Sirolimus

TAC Tacrolimus

ULN Upper Limit of Normal

Study Summary

Title	Liver Transplant Tolerance Enhanced By Sirolimus Therapy
Short Title	Sirolimus-Enhanced Tolerance
NU Protocol Number	STU00071766
Phase	Phase 4, pilot study
Methodology	Open label prospective study of Sirolimus withdrawal
Study Duration	18 months
Study Center(s)	Single-center
Objectives	Objectives: 1. To determine if tolerance can be achieved successfully in a reasonable percentage (>20%) of liver transplant (LT) recipients withdrawn from SRL monotherapy. 2. To investigate if blood/allograft metrics of immunoregulation correlate with successful SRL withdrawal in LT recipients.
Number of Subjects	25 Subjects meeting inclusion/exclusion criteria
Diagnosis and Main Inclusion Criteria	1) Adult LT recipients > 3 years post-LT and > 6 months on SRL monotherapy; 2) Primary living or deceased donor LT; 3) Consent to undergo full immunosuppression withdrawal (sirolimus [SRL] withdrawal)
Study Product, Dose, Route, Regimen	Sirolimus (patients on varying doses of daily oral tablet)
Statistical Methodology	The primary outcome will be the proportion of tolerant patients off SRL therapy with normal liver biochemistry and graft histology at 12 months. As a pilot study focused on acquiring preliminary data, there will be no control group maintaining SRL therapy or a control group withdrawing from different immunosuppressive therapy (i.e. calcineurin inhibitor [CNI] agents) as comparators. Immune assay changes with successful or failed withdrawal will also be compared with appropriate statistical tests.

This document is a protocol for a human research study. This study is to be conducted according to United States (US) and international standards of Good Clinical Practice (GCP); (Food and Drug Administration [FDA] Title 21, parts 312, 50, 56 and International Conference on Harmonization guidelines [ICH]), applicable government regulations and institutional research policies and procedures.

By signing below, I agree to conduct the research by US and International Standards of GCP FDA Title 21, parts 312, 50, 56 and ICH guidelines. Being the principal investigator (PI), I also agree to oversee that the subinvestigators and all research staff abide by the same standards and principles.

Name

Date

Introduction

This document is a protocol for a human research study. This study is to be conducted according to US and international standards of Good Clinical Practice (FDA Title 21 parts 312, 50, 56 and International Conference on Harmonization guidelines), applicable government regulations and Institutional research policies and procedures.

1.1 *Background*

The significance of this clinical trial lies in its potential to increase the success of immunosuppression (IS) therapy withdrawal in liver transplant (LT) recipients, thus decreasing the negative impact of IS on their long-term outcomes. Lifetime immunosuppression (IS) with standard agents, the calcineurin inhibitors (CNI) cyclosporine and tacrolimus (TAC), is currently required at clinically recommended doses and trough levels to prevent allograft rejection. However, this occurs at the significant expense of long-term CNI toxicity, i.e. chronic kidney disease (CKD), hypertension, hyperlipidemia, diabetes, infections and malignancy (1, 2). With improvements in early graft and patient survival, long term adverse IS effects have become increasingly important in this rapidly expanding patient population. The strategies to reduce long term CNI toxicity include dose minimization that still leaves patients on CNI therapy, conversion to non-CNI therapy, or even complete IS withdrawal. The second approach, conversion to non-CNI IS therapy, is attractive in the potential to stabilize or improve renal function and other CNI toxicities. One such non-nephrotoxic IS agent, the mammalian target of rapamycin inhibitor (mTOR-I) SRL, has a different mechanism of IS action and studies have shown that CNI to SRL conversion can stabilize renal dysfunction with a low risk of rejection (3, 4). Yet even with these possible benefits, patients on SRL are still subject to lifetime IS therapy with side effects and costs, highlighting the need to investigate the strategies that promote full IS withdrawal without rejection (3rd approach), also known as 'operational tolerance'.

Therefore, specific to this proposal and supported by our preliminary data, an additional advantage of mTOR-I therapy lies in its potential to promote such a clinical immunoregulatory state that could facilitate IS minimization and complete withdrawal. As the most immunoregulatory solid organ transplanted, the liver houses numerous extramedullary hematopoietic and non-immunogenic cells and secretes several immunoregulatory proteins (5). As a result, the percentage of LT recipients able to undergo IS withdrawal is the highest of all solid organ transplant recipients, although still only ~ 20% successful to date and primarily only performed in CNI-treated patients in withdrawal studies (6). This clinically unacceptable percentage is likely due to known CNI mechanisms inhibiting immunoregulation and the lack of available, well-defined immune monitoring to detect immunoregulation or unresponsive states. A key difference between mTOR-I and CNI is their effect on regulatory T cells (Tregs) and regulatory 'immature' dendritic cells (DCregs) important in the suppression of auto- and allo-immune responses. As an inhibitor of IL-2 signaling after T cell activation, SRL blocks proliferation of alloreactive T cells but promotes Tregs ($CD4^+CD25^{\text{high}}FOXP3^+$), regulatory cytokines (i.e. TGF- β 1), and tolerogenic dendritic cells (DCreg) (7, 8). In contrast, CNIs inhibit interleukin-2 (IL-2) transcription and thus negatively affect Treg generation (9-11). Importantly and most relevant to this proposal, we have recently demonstrated systemic (peripheral blood mononuclear cell [PBMC], bone marrow, allograft) Treg/DCreg increases and enhanced tolerogenic proteogenomic markers in LT recipients converted from CNI to SRL (12, 13), as well as augmented allo-specific Treg function by SRL vs. CNIs *in vitro* (14). These data provide the clinical and mechanistic background that support SRL facilitating operational tolerance in this pilot study.

The identification of biomarkers of tolerance is as important as the chosen IS regimen. Various reports demonstrate a high percentage of Tregs, DCregs, $\gamma\delta$ Tcells (V δ 1/V δ 2 ratio), and specific gene signatures in tolerant LT recipients (6, 15, 16). We have utilized a number of *in vitro* assays testing donor-specific

Treg inhibition/recruitment (Treg MLR) and regulation of cytotoxic T cells (micro-cell mediated lympholysis, m-CML) induced by IS therapies and in clinical tolerance trials (14, 17-20). Also, we have utilized peripheral blood/allograft immunophenotyping for regulatory cell populations and immunoregulatory proteogenomic assays to look for signatures of tolerance and CKD in LT recipients (13, 21). Yet the presence of Treg populations and differential gene array snapshots in 'already-withdrawn' patients or patients currently on IS therapy, without a clear understanding of their utility in monitoring during withdrawal, only provides circumstantial evidence for their role in tolerance. An array of assays performed throughout the tapering and withdrawal period, as described herein, would provide a more accurate measure of the effects of SRL on Treg function and immunoregulatory gene/protein expression, supporting their use as predictors of tolerance in future protocols.

With the above background and rationale, we expect to develop two strategies to promote the ability to achieve and monitor LT tolerance. The first is initial CNI to SRL conversion to promote systemic immunoregulation (already performed in our preliminary work (13)), followed by SRL minimization and withdrawal (this Institutional Review Board [IRB] submission). This is to be compared to the established literature success rate ($\approx 20\%$) of CNI withdrawal, as we do not feel it is clinically acceptable to include this as a control group (6). *We hypothesize that the clinical use of SRL promotes immunoregulatory pathways and provides higher IS withdrawal success compared to CNI therapy.* The second strategy aims to identify immunologic and proteogenomic assessments of immunoregulation, potentially enhanced by SRL conversion and predicting/correlating with successful IS withdrawal.

In summary, even though this is a small clinical/translational pilot study, it has a potential for significance in the field of transplant medicine. If successful, it could serve as a model approach for further studies and national grant funding in LT tolerance. Specifically, the Immune Tolerance Network (National Institutes of Health/National Institute of Allergy and Infectious Disease [NIH/NIAID]) requests these pilot data from our center prior to conducting a large multicenter controlled study of SRL (or other mTOR-I) withdrawal in LT recipients. The downstream impact could be far-reaching, not only from a clinical standpoint in improving patient outcomes, but also lead to amplified research in mechanisms of mTOR-I therapy, other tolerogenic approaches and biomarkers of tolerance. The immunoregulatory signatures determined preliminarily in this study could eventually, if validated, facilitate 'point-of-service' tests in clinical settings, either routinely or during modifications of therapy. Knowledge of such specific clinical and immunological characteristics and using an individualized approach would allow transplant clinicians to more accurately define and select appropriate candidates for withdrawal. This would satisfy our long term goal of developing a refined approach to more successfully withdraw IS therapy and improve outcomes for LT recipients.

1.2 Preclinical Data

Preliminary Data: We demonstrated that liver transplant (LT) recipients on SRL monotherapy had higher percentages of peripheral blood mononuclear cell (PBMC) immunophenotypic Tregs (CD4+CD25Hi+Foxp3+ cells) compared to recipients on CNIs (12). This led to a recently published CNI to SRL conversion trial demonstrating increased percentages of PBMC/bone marrow Tregs and PBMC DCregs (ILT3/4+) in LT recipients converted from tacrolimus to SRL monotherapy (13). Liver biopsy immunohistochemistry FOXP3:CD3 and CD4:CD8 ratios were significantly higher after conversion. Patient sera on TAC but not SRL suppressed Treg generation in mixed lymphocyte reactions. Finally, consistent with prior reports of genomic expression patterns and cellular assays as signatures of tolerance (16), we detected the expression of 289 novel genes and 22 proteins, several important in immunoregulatory pathways, after SRL conversion. In a separate in vitro study, we also demonstrated robust allospecific regulatory effects of SRL in Treg mixed lymphocyte reactions (14). Our preliminary data, in conjunction with other clinical and laboratory reports, provide the mechanistic rationale for the

concept that SRL may facilitate IS withdrawal in LT and that such assays should be tested in parallel as biomarkers of tolerance. We hypothesize that SRL will promote regulatory gene/protein expression patterns in the peripheral blood AND in the allograft, which can then be utilized as predictive assays in tolerance trials. To robustly test this hypothesis, we will collect serial blood and allograft samples before/after withdrawal and at the time of biopsy for possible rejection, all to be tested as markers of immunoregulation. This will consist of assays similar to those performed in our recent work (12, 13, 21).

1.3 Clinical Data to Date

We and others have shown the safety of CNI to SRL conversion (3, 4, 12, 13), but there are no current studies testing full IS withdrawal in patients on SRL monotherapy. There are numerous studies of CNI withdrawal that have shown together an approximate 20% success rate (6). Fortunately, the risk of graft failure due to rejection in all of these prior withdrawal studies was extremely low (<1%) (6), making withdrawal a reasonably safe option. However, even so, 20% success is not considered clinically high enough to be acceptable as a standard of care approach and few centers, if any, are withdrawal patients routinely from IS therapy because of this low rate, except for in the setting of aggressive malignancy, infection or post-transplant lymphoproliferative disorder (PTLD). Thus, our goal is that SRL will be associated with higher than 20% success, allowing further study of this approach to make IS withdrawal clinically more feasible and acceptable to clinicians.

1.4 Dose Rationale and Risk/Benefits

All our LT patients are on different doses of SRL therapy currently (on average 1-2 mg daily) and will be tapered off of SRL according to the study procedures. There is no new drug therapy introduced in this study. It is hypothesized that 50% (vs. 80% historical CNI withdrawal) will develop reversible rejection during either minimization or withdrawal of SRL, requiring reinstatement of immunosuppressive therapy (i.e. failure of withdrawal). Fortunately, previous studies involving withdrawal of IS in LT recipients (mainly from CNI therapy) have shown that patients who fail to withdraw and develop rejection have a minimal (<1%) risk of graft failure when IS reinstated (6). Only one patient in the major withdrawal studies developed chronic rejection and required retransplantation. Thus it is, in the vast majority, reversible. This may not be the case with SRL therapy although none of our previously SRL converted patients developed rejection or lost their grafts. Therefore, we feel the risk of withdrawal, while not insignificant, is fairly low in comparison to the high potential for benefit of being completely withdrawn from IS therapy altogether, satisfying the concept of clinical equipoise. All of these risks and benefits will be discussed with the patient at the time of informed consent. For IS withdrawn patients in our study, we expect at minimum stability or improvement in all of the secondary outcomes related to chronic IS therapy. For liver biopsies on all patients, the risk includes the following: bleeding, infection, perforation of an organ surrounding the liver (all < 1%). The patient will undergo a separate informed consent (for the procedure and is different than the actual study consent) prior to all liver biopsies. We feel that liver biopsy is necessary so that the patient will not proceed into the trial if any histological graft dysfunction or rejection is detected on biopsy. While liver biopsy is invasive and has associated risks, they are outweighed by the benefit of knowledge of liver histology prior to the intervention and follow-up. Decisions on whether to undergo the intervention can therefore be more accurately determined and provide more safety than risk to the patient. All of these risks will be clearly discussed with the patient during the study process and documented by appropriate consents.

2 Study Objectives

Primary Objective: The goal is to determine if operational tolerance (normal graft function without IS therapy x 12 months) can be achieved successfully in LT recipients withdrawn from SRL.

Secondary Objectives

1. To investigate if cellular, allograft and proteogenomic metrics of immune regulation are predictive of and persist following successful SRL withdrawal in LT recipients.
2. To analyze any initial clinical benefit of minimization and withdrawal of SRL therapy.

3 Study Design

3.1 General Design

Study Overview

The study proposed is a prospective trial of controlled SRL monotherapy minimization and withdrawal in up to 25 stable non-immune non-viremic LT recipients. Given the sample size calculations (see Statistical section), we plan to enroll up to 25 SRL monotherapy patients for this study (Figure 1). All patients will be consented to undergo laboratory evaluation as well as an enrollment liver biopsy and blood tests. If the patient meets inclusion/exclusion (I/E) criteria (see below), SRL will be minimized over 6 months until once a week dosing is achieved. Repeat clinical and immunological blood tests as above will be performed, and if no biochemical signs of rejection, SRL will be discontinued with blood tests and liver biopsy 12 months later for similar biochemical, histological and immunological measures. At any concern for rejection, liver biopsy and assays for equivalent biochemical, histological and immunological measures will be performed and if rejection is diagnosed on biopsy, a second attempt at withdrawal **will not** be performed. Patients will be monitored as standard of care with clinic visits every 6 months and laboratory tests every 2 weeks. The total study length will be 18 months: 6 month minimization phase and 1 year follow-up after withdrawal success/failure. The primary outcome will be the proportion of tolerant patients off SRL therapy with normal liver biochemistry and graft histology at 18 months. Secondary outcomes will include the incidence, severity and reversibility of rejection, patient/graft survival, resolution of SRL and other non-specific IS effects, and the assessment of clinical/immunological biomarkers of tolerance. All continuous/categorical clinical variables will be compared with the appropriate statistical analyses. The goal is that the primary and secondary aims will provide valuable preliminary data to further elucidate the mechanisms of mTOR-I immunoregulation and for determining the initial clinical success/feasibility of the mTOR-I approach (vs. historical 20% CNI withdrawal success seen in studies from the Immune Tolerance Network [ITN] and other groups). This is all so as to guide a submission to the Immune Tolerance Network for larger, more adequately powered prospective trials comparing SRL vs. CNI withdrawal and accompanying biomarker predictors of tolerance. If this pilot study fails to show a correlation between our biomarkers and the success/failure of SRL withdrawal, or is associated with an unacceptable low (e.g. <20%) rate of operational tolerance, then this would avoid the necessity for such large, expensive trials and support the continued development of alternative approaches to tolerance.

Consent and Initial Phase of Enrollment (see Study Protocol Figure- Appendix A)

These liver transplant candidates (up to 25 SRL) will be approached for consideration and informed consent into the study. The consent form will include discussion of the risks/benefits of their current therapy (SRL) and the planned minimization/withdrawal. Specifically, the risks of minimization/withdrawal (i.e. developing acute or chronic rejection, alloimmune hepatitis during any portion of the study), although unlikely, will be a major emphasis of the consent process. The consent form will also include the strict requirement for patients to follow all instructions from the PI in regard to the close laboratory follow-up occurring throughout the trial, to diagnose any episode of rejection or concern as early as possible to be able to respond appropriately. All of the study procedures will be discussed with the patient during clinic visits. They will be informed that neither participation nor refusal will influence their clinical care. All laboratory tests or costs related to their care in the study, with the exception of non-standard of care items (i.e. liver biopsies, blood assays), will be the responsibility of the

patient and/or his/her insurance company. They will be asked questions afterwards to verify comprehension and then sign the consent form documenting their agreement to participate. A signed copy of the consent form will be given to them. Participation is completely voluntary and they may discontinue participation the study at any time without affecting their care or participation in any other study. No financial compensation will be given.

Screening Evaluation at Enrollment (see Study Protocol Figure)

After long term (> 3 years post-LT, > 3 months on SRL monotherapy) on SRL monotherapy, inclusion/exclusion criteria will be reviewed and if appropriate, consent as above will be obtained. If the patient agrees and signs consent, baseline standard of care screening laboratories complete blood count, comprehensive metabolic panel, sirolimus (CBC, CMP, SRL trough level, fasting lipid profile, hemoglobin A1C [HbA1C], urine protein/creatinine ratio) and non-standard of care biomarker assays (blood immunophenotyping, proteogenomics) and liver biopsy (histology and graft immunohistochemistry) will be performed as dictated by the protocol. In addition, the liver biopsy will be used to determine stability in graft function (i.e. no evidence of rejection or immune-mediated hepatitis) before considering minimization/withdrawal. SRL minimization/withdrawal will only be performed if clinically, biochemically and histologically [by biopsy; liver transplant pathology read ([name], [name])] stable. Throughout the entire study, liver function tests will be monitored every 2 weeks (monthly is standard of care, so the interim non-standard of care 2 week blood tests will be covered by the study funds). Patients entering the minimization/withdrawal phases will be reduced by a total dose of 50% of their baseline dose every month until patients are on 0.5 mg SRL daily. At this point, every other day dosing will begin x 1 month. If no LFT abnormalities, twice weekly dosing x 1 month, then once a week dosing x 1 month. Prior to complete discontinuation, repeat clinical (screening labs above) and blood biomarker assays (blood immunophenotyping, proteogenomics) will be performed. Liver biopsy will not be performed at this juncture unless there are biochemical signs of liver injury. If complete withdrawal is deemed safe (no evidence of biochemical abnormalities) patients will be withdrawn completely (i.e. the once/week SRL dose discontinued) and followed off IS therapy for one year. In this time period, liver function tests will be monitored every 2 weeks, as usual, and repeat clinical (screening labs above), liver biopsy and blood (blood immunophenotyping, proteogenomics) assays performed at the end of this year or at any concern for rejection.

Blood and Tissue Samples

Standard of care laboratories (CBC, CMP) will be performed every month on all patients, and only LFTs performed in the interim 2 weeks between each month (non-standard of care; covered by the study funds) until complete withdrawal. 3 green top 5 mL and 3 red top 5 mL tubes of blood for biomarker assays will be taken on all patients prior to study enrollment, prior to complete withdrawal, and one year after withdrawal or at the time of suspected rejection. Liver biopsy (one 3 cm biopsy- 2 cm for histology and 1 cm for genomic assays) will be performed at baseline (pre-minimization) and 1 year post withdrawal. A separate clinical informed consent will be obtained each time a liver biopsy is performed. If the patient develops elevation in liver transaminases requiring a liver biopsy at any stage of the study protocol, blood (all for immune monitoring (IM) assays) will be requested from the patient at the time of the biopsy. If rejection occurs, the patient will be followed in the study until completion but not be further withdrawn from SRL or have a liver biopsy at the end of the study

Follow-up

Laboratory follow-up is described above- every 2 weeks throughout the trial until complete withdrawal. Any biochemical (or clinical) signs or significant liver function test abnormalities will be acted on immediately either by liver biopsy or a pause in IS withdrawal per investigator discretion. All patients will be seen in the clinic every 3 months to assess for any new signs or symptoms or resolution of drug side effects in the minimization or withdrawal arm. Quality of life questionnaires; Post Liver Transplant

Quality of Life Instrument (pLTQ) and the Promis-29 profile v1.0 will be administered at the study onset and after successful vs. unsuccessful withdrawal (end of study)

Outcome Measures

The primary outcome will be the proportion of patients off SRL therapy with normal liver biochemistry and graft histology at 12 months (i.e. tolerant). Thus, the incidence of graft dysfunction (acute rejection, immune mediated or autoimmune hepatitis, chronic rejection) or non-tolerance will be assessed in this SRL withdrawal group and compared to the historical CNI group (20% tolerant; 80% failure) as the primary endpoint. This rate will be a composite of the cumulative number of biopsy-proven graft dysfunctions requiring conversion back to SRL or additional IS therapy or discontinuation of minimization/withdrawal that occur during the course of the study. Major secondary measures compared will be the predictive capacity of the blood and graft biomarker assays (immunophenotyping, genomic/proteomics) before and after minimization/withdrawal in the success vs. failure groups. Clinical secondary outcomes will be compared: the number of infectious complications, liver biopsy complications, cardiovascular outcomes (i.e. blood pressure, diabetes control, lipid levels), renal function, hematopoietic parameters, gastrointestinal effects, or other side effects of SRL that may or may not improve or develop with minimization/withdrawal. These will all be documented by a study database during patient visits, electronic charts and/or by phone communication. Finally, quality of life (Post Liver Transplant Quality of Life Instrument (pLTQ) and the Promis-29 profile v1.0) will be analyzed at the end of the study to determine the effect of IS minimization/withdrawal on other health benefits.

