4.3 Subject Recruitment and Screening

Recruitment and Informed Consent

Nonimmune, nonviremic liver transplant patients on SRL therapy meeting I/E criteria (except for liver biopsy which will be performed only if all other I/E criteria met) will be approached consideration and informed consent into the study. The consent form will include discussion of the risks/benefits of their current therapy (SRL) and the planned minimization/withdrawal. Specifically, the risks of minimization/withdrawal (i.e. developing acute or chronic rejection, alloimmune hepatitis during any portion of the study) and procedural risks will be a major emphasis of the consent process. The consent form will also include the strict requirement for patients to follow all instructions from the PI in regard to the close laboratory follow-up occurring throughout the trial, to diagnose any episode of rejection or concern (elevation of liver transaminases) as early as possible to be able to respond appropriately. All of the study procedures will be discussed with the patient during clinic visits. They will be informed that neither participation nor refusal will influence their clinical care. All laboratory tests or costs related to their care in the study, with the exception of non-standard of care items (i.e. liver biopsy, IM assays), will be the responsibility of the patient and/or his/her insurance company. They will be asked a few questions afterwards to verify comprehension and then sign the consent form documenting their agreement to participate. A signed copy of the consent form will be given to them. Participation is completely voluntary and they may discontinue participation in either study at any time without affecting their care.

Screening Evaluation at the time of Minimization/Withdrawal

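### Section 3.1 calls rejection unlikely in its description of consent, while section 1.4 expects it in half of the patients

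*Combined protocol and SAP*

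**What the plan says.** Four places in the protocol bear on how likely rejection is and what is said about it at consent.

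- **Section 3.1, Consent and Initial Phase of Enrollment.** The risks of minimization and withdrawal, among them acute or chronic rejection and alloimmune hepatitis at any time in the study, "although unlikely, will be a major emphasis of the consent process".
- **Section 1.4, Dose Rationale and Risk/Benefits.** "It is hypothesized that 50% (vs. 80% historical CNI withdrawal) will develop reversible rejection during either minimization or withdrawal of SRL". The sentence goes on to say that these patients need immunosuppression reinstated and count as withdrawal failures. The same section puts graft failure after reinstatement at under 1%, from mainly CNI studies. It warns that this may not carry over to sirolimus, and it undertakes to discuss the risks and benefits at consent.
- **Section 3.1, Outcome Measures.** The result is to be "compared to the historical CNI group (20% tolerant; 80% failure) as the primary endpoint". Section 1.3 also gives about 20% success for CNI withdrawal.
- **Section 4.3, Recruitment and Informed Consent.** The consent paragraph recurs almost unchanged, but here the same risks "and procedural risks will be a major emphasis of the consent process". No likelihood is attached.

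**The concern.** Rejection is the principal foreseeable harm of this elective withdrawal in stable patients, and the main way to fail the primary endpoint. It also ends the attempt: immunosuppression is restarted and no second withdrawal is made. Section 1.4 rests its case for equipoise on weighing this risk against the benefit of being free of immunosuppression.

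The paragraph that sets out what the consent form must cover attaches a likelihood to that risk, and the likelihood disagrees with the rate hypothesized in section 1.4. If the phrase were carried into the consent form or the consent discussion, the patient would be weighing a different risk from the one the design assumes. An IRB or investigator reading section 3.1 alone would also take away the wrong expectation.

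**Working it through.** This is a comparison of words with figures. There is no power or alpha calculation to reproduce.

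**Inputs**

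| Input | Value | Source |
|---|---|---|
| Likelihood of acute or chronic rejection, alloimmune hepatitis | unlikely | 3.1, consent paragraph |
| Hypothesized rejection, sirolimus withdrawal | 50% | 1.4 |
| Historical CNI withdrawal | 80% rejection (1.4); 80% failure, 20% tolerant (3.1) | 1.4; 3.1, Outcome Measures |
| Graft failure after rejection, immunosuppression reinstated | <1% | 1.4 |
| Planned enrolment | up to 25 | 3.1 |

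**Step 1: the historical figure.** 1 - 0.20 = 0.80, so the 80% in section 1.4 agrees with the 20% success in section 1.3 and the 20%/80% split in section 3.1. The 50% is a stated hypothesis with no derivation.

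**Step 2: same event, same period?** The consent paragraph covers any portion of the study and names acute rejection. Section 1.4 covers rejection during either minimization or withdrawal. The two statements overlap on the event that matters.

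**Step 3: expected number.** n x p = 25 x 0.50 = 12.5 patients. With a binomial count at n = 25 and p = 0.50, the central 95% range is 8 to 17, and the chance of at least 8 rejections is 0.978. Twenty-five is a ceiling: enrolment is up to 25, and patients whose enrolment biopsy is not stable do not enter the taper. A smaller number tapered lowers the count but leaves the proportion at one half.

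**Step 4: is a lower rate given anywhere?** No. Section 1.4 notes that none of the centre's converted patients rejected, but that concerns conversion to sirolimus, not stopping it. Section 1.3 says that no current studies test full withdrawal from sirolimus monotherapy.

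**Step 5: which outcome is rare?** Sections 1.3 and 1.4 give under 1% for graft failure. Section 3.4 calls patient or graft loss very unlikely. Section 1.4 mentions a single patient in the major withdrawal studies with chronic rejection leading to retransplantation. None of these describes acute rejection.

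**The case against.** **The phrase may have been meant for graft loss or severe rejection.** This is plausible. Section 3.4 uses similar words for patient and graft loss, and the stopping rule in section 8.4 is triggered by steroid-resistant or chronic rejection in more than 10% of subjects. But the sentence in section 3.1 names acute rejection and does not mention graft loss. If the narrower meaning was intended, the text has to say so.

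**The 50% is only a hypothesis.** True. It is nevertheless the only rate the protocol offers for sirolimus withdrawal, and the historical figure beside it is higher.

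**Section 1.4 already commits to disclosure.** It says that all of these risks and benefits will be discussed at consent, and a natural reading includes the rejection risk given earlier in the same paragraph. Sections 3.1 and 4.3 also require a check of comprehension before signature. This stands as mitigation. It does not settle the matter, because the 50% is not named as something to be disclosed.

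**Stronger readings a reader might infer.**

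- *Patients are told that rejection is unlikely.* The documents do not show this. The phrase is an aside in protocol text, the instruction in that sentence is to emphasize these risks, and the consent form was not available for review.
- *Patients would not see why laboratory follow-up matters.* Section 3.1 has the form state the follow-up requirement together with its purpose, early diagnosis of rejection.
- *The two consent descriptions contradict each other.* Section 4.3 is silent on likelihood, which is a difference in wording and not a contrary statement.
- *Twenty of 25 patients are expected to reject.* That applies the historical CNI rate to sirolimus patients. The protocol does not expect it, and section 3.1 uses the 80% for a failure outcome broader than rejection.

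**Conclusion.** The inconsistency is real and confined to the stated likelihood. Section 3.1 labels as unlikely a set of risks that includes acute rejection, while section 1.4 expects rejection in one patient in two: 12 to 13 patients if all 25 are tapered. The rare outcome in the protocol is graft failure, and that figure comes with its own caveat for sirolimus.

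The size rests on the protocol's unsupported 50% and on all 25 patients entering the taper. The conflict needs only the 50%. It changes no endpoint, analysis or monitoring step. It is still worth correcting, because it misstates the main harm in the section that specifies consent content. Whether it reaches patients cannot be judged from these documents.

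**What to change.** 1. In section 3.1, delete the phrase on likelihood, or restrict it explicitly to graft loss.
2. State the protocol's own expectation there: about 50% to develop rejection and need immunosuppression reinstated, beside about 80% historical failure with CNI withdrawal.
3. Give the graft-failure figure separately: under 1%, from mainly CNI studies, with section 1.4's caveat that this may not hold for sirolimus.
4. Use the same wording in section 4.3, and name the 50% in section 1.4's commitment to discuss risks at consent.
5. Check that the consent form matches. Section 10 says that a copy follows the protocol, so the sponsor can do this directly.

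The cost is a wording amendment with IRB review and possibly slightly slower recruitment. No procedure or analysis changes.
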